6.2. Preparation/Handling/Storage/Accountability

Upon arrival of the study drug at the study site, the study drug kits should be removed from the shipping container and stored in their original cartons under refrigerated conditions at 2°C to 8°C (35°F to 46°F) and protected from light. Study drugs should not be frozen.

Study drugs must be stored in a secure, limited-access storage area with temperature monitored daily.

Infusions of study drug should be prepared using aseptic technique. Ravulizumab and placebo need to be further diluted in a 1:1 ratio with 0.9% sodium chloride. Ravulizumab and placebo will be filtered with a 0.2 micron filter during infusion.

- The Investigator or designee must confirm appropriate temperature conditions have been maintained during transit for all study drug received and any discrepancies are reported and resolved before use of the study drug.
- Only participants enrolled in the study may receive the study drug and only authorized site staff may supply or administer the study drug. All study drug must be stored in a secure, environmentally controlled, and monitored (manual or automated) area in accordance with the labeled storage conditions with access limited to the Investigator and authorized site staff.
- The Investigator, institution, or the head of the medical institution (where applicable) is responsible for study drug accountability, reconciliation, and record maintenance (ie, receipt, reconciliation, and final disposition records).
 - This responsibility includes the reporting of any product complaints to [contact] within 1 business day. A product complaint is defined as any written, electronic, or oral communication that alleges deficiencies related to the identity, quality, durability, reliability, usability, safety, effectiveness, or performance of a product or clinical study material and/or its packaging components after it is has been released for distribution to an end customer that affects the performance of such product.
 - The pharmacist or other designated individual will maintain records of study intervention delivered to the study site, the inventory at the study site, the distribution to and use by each participant, and the return of materials to the Sponsor for storage or disposal/destruction of materials at the study site. These records should include dates, quantities, batch/serial numbers, expiration dates, in-clinic temperature log, and unique code numbers assigned to the study intervention and study participants.
 - The Investigator will maintain records that adequately document that the participants were administered the correct study treatment kits and reconcile the products received from the drug dispensing center. Investigational product will not be returned to the Sponsor or disposed of until accountability has been fully monitored.
- Further guidance regarding preparation, handling, storage, accountability and final disposition of unused study drug is provided in the Pharmacy Manual.

6.3. Measures to Minimize Bias: Randomization and Blinding

6.3.1. Randomization

Participants will be randomized on Day 1 after the Investigator has verified that they are eligible. All eligible participants will be randomly assigned to ravulizumab or placebo in a 2:1 ratio using Interactive Response Technology (IRT).

To balance the effects of potential confounding factors between the ravulizumab and placebo arms, randomization will be stratified by whether corticosteroid induction treatment was initiated prior to Screening versus during the Screening Period for participants in the LN cohort and by mean proteinuria (1 to 2 g/day versus > 2 g/day) from 2 valid 24-hour urine collections during the Screening Period for participants in the IgAN cohort.

6.3.2. Blinding

Participants, all investigative site personnel, and any Alexion employee, or designee, directly associated with the conduct of the study will be blinded to participant treatment assignments during the Initial Evaluation Period. The blinding will be maintained by using identical study drug kits and labels for ravulizumab and placebo. The placebo will have an identical appearance to that of ravulizumab. The randomization code will be maintained by the IRT provider.

The primary endpoint evaluation will occur for each disease-specific cohort after all participants in the disease-specific cohort complete the Week 26 Visit or withdrawn from the study prior to Week 26. Alexion will be unblinded at this time to conduct the primary analysis.

After completion of the Initial Evaluation Period, participants in the LN cohort will continue receiving their randomized study drug and both the participants and the investigative site personnel will remain blinded for the remaining 24-week Extension Period. For the IgAN cohort, participants in the placebo group will switch to receive a blinded loading dose of ravulizumab after completion of the protocol-required assessments at the Week 26 Visit and participants in the ravulizumab group will receive a blinded ravulizumab dose of 900 mg at Week 26. The 900 mg dose at Week 26 was chosen to ensure maintenance of complete C5 inhibition until the next scheduled maintenance dose. Following completion of the Week 26 Visit, participants in the IgAN cohort will receive open-label ravulizumab treatment during the 24-week Extension Period.

In case of an emergency, the Investigator has the sole responsibility for determining if unblinding of a patient's intervention assignment is warranted. Patient safety must always be the first consideration in making such a determination. If the Investigator decides that unblinding is warranted, the Investigator will be able to unblind the patient's treatment allocation directly using the IRT. If a patient's intervention assignment is unblinded, the Sponsor must be notified within 24 hours after breaking the blind. The date and reason that the blind was broken must be recorded in the source documentation, as applicable.

When an AE is unexpected or related and serious, the blind will be broken for that specific participant only. The blind will be maintained for persons responsible for the ongoing conduct of the study (such as the management, monitors, Investigators, etc) and those responsible for data analysis and interpretation of results, such as biometrics personnel.

Unblinded information will only be accessible to those who need to be involved in the safety reporting to Health Authorities, Independent Ethics Committees (IECs), and/or Institutional Review Boards (IRBs).

Any participant who is unblinded during the Initial Evaluation Period will be withdrawn from the study.

Investigators will receive only blinded information unless unblinded information is judged necessary for safety reasons.

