3.2.3. Suboptimal Response (LN Cohort Only)

A Suboptimal Response is determined in the opinion of the Investigator in addition to the following criteria after the Week 26 Visit:

- Reproducible proteinuria $\leq 25\%$ decreased compared to baseline based on UPCR on a 24-hour urine collection performed by the central laboratory

Reproducibility of proteinuria requires that the proteinuria based on a UPCR from a spot urine collection is confirmed by a central laboratory UPCR calculated on a 24-hour urine collection obtained within a 2-week period.

Participants with Suboptimal Response must be discussed with the Investigator and Medical Monitor. Participants with Suboptimal Response will stay in the study and continue to receive study drug. Intensification of current standard of care or introduction of new immunosuppressive therapies are allowed per the clinical discretion of the Investigator in conversation with the Medical Monitor and will be considered additional standard of care therapy.

Participants with Suboptimal Response will be included as Treatment Failure.

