^a Dose regimen will be based on the participant's most recently recorded body weight. Contact the Alexion Medical Monitor if a participant's weight drops below 40 kg during the study treatment period (Initial Evaluation Period or the Extension Period).

^b Blinded dose on Day 183 (Week 26) for participants who were randomized to the ravulizumab group and are entering into the Extension Period.

^c Blinded loading dose on Day 183 (Week 26) for participants who were randomized to the placebo group and are entering into the Extension Period.

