9.5.2. Interim Analysis for Primary Endpoint

The primary efficacy analysis will be performed for each disease-specific cohort at the end of the 26-week Initial Evaluation Period after all participants in the disease-specific cohort have completed or withdrawn from the 26-week Initial Evaluation Period. This analysis will allow for evaluation of the primary endpoint and Phase 3 planning and will have no impact on the progression of this study.

In addition, an early interim analysis may be conducted for either disease cohort at the discretion of Alexion (based on feasibility) when at least 50% of participants have been randomly assigned to study treatment and have had the opportunity to complete the 26-week Initial Evaluation Period. These interim analyses, if performed, will be conducted by a separate unblinded team to preserve the integrity of the study design and minimize risk of bias. The interim analysis for the IgAN cohort will be for Phase 3 planning purposes only with no impact on the progression of the study. The interim analysis for the LN cohort will not include hypothesis testing and will not impact the progression of the study.

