1. INTRODUCTION

This Statistical Analysis Plan (SAP) describes the statistical methods for analyzing data for Protocol ALXN1210-NEPH-202, “A Phase 2, Double-Blind, Randomized, Placebo-Controlled Study to Evaluate the Efficacy and Safety of Ravulizumab in Adult Participants With Proliferative Lupus Nephritis (LN) or Immunoglobulin A Nephropathy (IgAN).” Standard data presentation instructions and table, figure, and listing specifications are contained in the Data Presentation Plan (DPP) in a separate document.

The primary efficacy analysis will be performed for each disease-specific cohort at the end of the 26-week Initial Evaluation Period after all participants in the disease-specific cohort have completed or withdrawn from the 26-week Initial Evaluation Period. This analysis will allow for evaluation of the primary endpoint and Phase 3 planning and will have no impact on the progression of this study. The sponsor will be unblinded at this time to conduct the primary analysis. After completion of the Initial Evaluation Period, participants in the LN cohort will continue receiving their randomized study intervention, and both the participants and the investigative site personnel will remain blinded for the remaining 24-week Extension Period. In the IgAN cohort, participants in the placebo treatment group will switch to receive a blinded loading dose of ravulizumab at Week 26 and participants in the ravulizumab treatment group will receive a blinded ravulizumab dose of 900 mg at Week 26. Starting at Week 28, all participants in the IgAN cohort will receive open-label weight-based doses of ravulizumab once every 8 weeks (q8w) until the end of the Extension Period.

The final analysis will occur at the end of the study when all participants have completed the Post-treatment Follow-up Period or withdrawn from the study early and will include all planned analyses that will be presented in the final Clinical Study Report.

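### After the LN Week 26 analysis the plan does not keep the sponsor's Medical Monitor blinded to individual assignments, although that role is consulted on therapy that sets Week 50 outcomes

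*Protocol*

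**What the plan says.** **Who is blinded, and until when.** Protocol 6.3.2 states that participants, site personnel and sponsor staff directly involved in conduct "will be blinded to participant treatment assignments during the Initial Evaluation Period". Once everyone in a cohort has completed the Week 26 Visit or withdrawn, "Alexion will be unblinded at this time to conduct the primary analysis". SAP section 1 repeats this: "The sponsor will be unblinded at this time to conduct the primary analysis". For LN after that point, Protocol 6.3.2 says "both the participants and the investigative site personnel will remain blinded for the remaining 24-week Extension Period". Neither document exempts a sponsor role or describes an access restriction.

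**The Medical Monitor.** A footnote to Table 9 in Protocol 6.1 ("Contact the Alexion Medical Monitor") identifies the role as the sponsor's. Under Protocol 3.2.3, intensified or new therapies for Suboptimal Response after Week 26 "are allowed per the clinical discretion of the Investigator in conversation with the Medical Monitor". Protocol 6.6 goes further: any use of additional standard of care therapy in LN should be discussed between the Investigator and the Medical Monitor.

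**Where a firewall exists.** Protocol 9.5.2 says that the optional early interim analyses "will be conducted by a separate unblinded team to preserve the integrity of the study design and minimize risk of bias". SAP 5.8.2 and 5.8.3 also specify a separate unblinded team. SAP 5.8.4, on the Week 26 analysis, does not. The Protocol synopsis states that there is no data monitoring committee.

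**The concern.** The LN cohort stays on randomised, blinded treatment to Week 50, so the LN extension is meant to yield between-arm comparisons. Over the same period the plan places no blind on a sponsor role that takes part in conversations about rescue. Someone who knows the assignment, even in an advisory role, could affect who receives additional therapy or when, without intending to. Receipt of that therapy then counts directly in several Week 50 outcomes. At stake is the credibility of those comparisons, not the primary result.

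Elsewhere the plan protects the LN blind to Week 50. For example, footnotes to Tables 1 and 3 bar site staff from viewing complement immunohistochemistry before then. The gap is on the sponsor's side.

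**Working it through.** The plan gives no figure on this point to reproduce. The check is a reading of the text, followed by an estimate of how many participants could be exposed.

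**Step 1: does any sentence keep the Medical Monitor blinded after the LN Week 26 analysis?**
- The sponsor-staff blind in Protocol 6.3.2 ends with the Initial Evaluation Period.
- The unblinding sentences in Protocol 6.3.2 and SAP section 1 name the sponsor as a whole and exempt nobody.
- The continuing LN blind names participants and site personnel only.
- A later paragraph of 6.3.2 keeps conduct staff blinded, but it follows the sentence on breaking the blind for one participant's adverse event. It also keeps biometrics staff blinded, so it cannot describe the Week 26 analysis.

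The answer is no. Nor does any sentence say that the Medical Monitor is unblinded. The accurate statement is that the plan does not keep that role blinded.

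**Step 2: which Week 50 LN outcomes depend on receipt of additional therapy?**
- Treatment Failure is receipt of that therapy (Protocol 3.2.4, SAP 5.4.11).
- CRR and PRR require no Treatment Failure (Protocol 3.2.5), and recipients are nonresponders (SAP 5.1.4, 5.4.4, 5.4.5).
- Proteinuria and eGFR after receipt are replaced by the value at the event in one planned MMRM and treated as missing in the other (SAP 5.4.1, 5.4.2).
- Time to UPCR of 0.5 g/g or below is censored at receipt (SAP 5.4.6).

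**Step 3: how many participants could be exposed?** Unblinding is triggered when the last LN participant completes Week 26 or withdraws. Those still short of Week 50 were randomised in the last 24 weeks of enrolment (50 − 26 = 24). With uniform accrual over A weeks and a lag of L weeks from trigger to unblinding:

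exposed fraction = (24 − L) / A; exposed number = 60 × (24 − L) / A

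The cohort size of 60 and the 24 weeks come from the Protocol. A, L and uniform accrual are assumptions.

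| A (weeks) | L = 0 | L = 8 | L = 16 |
|---|---|---|---|
| 52 | 24/52 = 46%, 27.7 | 16/52 = 31%, 18.5 | 8/52 = 15%, 9.2 |
| 104 | 24/104 = 23%, 13.8 | 16/104 = 15%, 9.2 | 8/104 = 8%, 4.6 |
| 156 | 24/156 = 15%, 9.2 | 16/156 = 10%, 6.2 | 8/156 = 5%, 3.1 |
| 208 | 24/208 = 12%, 6.9 | 16/208 = 8%, 4.6 | 8/208 = 4%, 2.3 |

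The zero-lag column is an upper bound for each accrual length, and a lag of 24 weeks or more would leave nobody exposed. Only those who then face a rescue decision could actually be affected. The documents do not allow that smaller number to be estimated.

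**The case against.** The case on the other side is substantial.

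- **The unblinding has a stated purpose.** The sponsor is unblinded to conduct the primary analysis, which need not mean that every employee sees allocations. A reader might infer that the Medical Monitor will be unblinded; no sentence says so. This stands, and it is why the point is framed as a missing protection.
- **The masking that the protocol claims stays in place.** The synopsis lists participant, Investigator and outcomes assessor as blinded, not the sponsor. A reader might conclude that the double-blind claim fails, or that all Week 50 LN comparisons are compromised. The documents support neither. LN participants and sites stay blinded, and the route runs only through rescue.
- **The Investigator decides, and much of the evidence is objective.** Suboptimal Response needs central laboratory confirmation. Renal Flare criteria are largely laboratory-based, and the Medical Monitor is notified of such flares. Therapy for an Extrarenal SLE Flare rests on the Investigator's judgement. The Medical Monitor's part is therefore advisory, but Protocol 6.6 still brings that role into every use of additional therapy. Protocol 3.2.3 also appears to count Suboptimal Response itself as Treatment Failure, whereas 3.2.4 ties failure to receipt of therapy. Those two sections need reconciling; the SAP follows receipt.
- **The endpoints are descriptive secondaries in a Phase 2 study.** This limits the consequence. However, the SAP still plans a Week 50 proteinuria contrast with a 90% CI, a CMH test for CRR and a log-rank test, and bias shifts an estimate whether or not alpha is spent on it.
- **Sponsor unblinding is deliberate, for Phase 3 planning.** That purpose does not require the people who talk to sites about individual LN participants to hold their assignments.

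**Conclusion.** The concern holds in a limited form. As written, the plan lifts the sponsor blind at the LN Week 26 analysis and leaves the Medical Monitor and site-facing sponsor staff with no stated blind during the rest of the LN extension. This creates a route to bias in Week 50 LN comparisons that depend on additional therapy. It does not show that bias will occur.

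Not affected are the Week 26 primary endpoint, the whole IgAN cohort and LN participants already past Week 50 at unblinding. The exposed group is at most about 28, 14 or 9 of 60 for 1, 2 or 3 years of uniform accrual with no lag. It falls to about 9 down to 2 if unblinding takes 16 weeks and accrual runs 1 to 4 years. These counts rest on assumed accrual and lag, which the documents do not give.

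The text is clear about what is and is not protected. The one inferred step is that unblinding the sponsor could include its Medical Monitor. The point is worth correcting because the remedy is cheap and the plan already accepts the principle for its early interim analyses.

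**What to change.** Amend Protocol 6.3.2 and SAP sections 1 and 5.8.4 to state that:

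1. the LN Week 26 analysis is run by sponsor personnel with no part in ongoing LN conduct, such as the separate unblinded team already described in Protocol 9.5.2; and
2. the Medical Monitor and all site-facing sponsor staff stay blinded to individual LN assignments, and receive no by-participant treatment listings, until the LN Week 50 database lock.

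No change to visits, data collection or sample size is needed. The cost is wording plus a small access-control burden. There is one real restriction. SAP 5.8.4 includes all planned safety analyses at Week 26, and SAP 5.6 provides safety listings by participant and treatment group. Those unblinded LN outputs would have to be withheld from conduct staff until the Week 50 lock. The separate analysis team could still use them.

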6.4. Study Drug Compliance

During this study, participants in both cohorts will receive all study drug infusions under the supervision of the Investigator, or designee.

The date and time of each dose administered will be recorded in the source documents and in the CRFs.

The dose of study drug and study participant identification will be confirmed at the time of dosing by a member of the study site staff other than the person administering the study drug.

6.5. Allowed Concomitant Therapy

Information regarding prior use of disease-specific treatment, including immunosuppression induction treatment for participants in the LN cohort, and ACE inhibitors and/or ARBs for participants in the IgAN cohort, will be documented in CRF.

All information regarding allowed concomitant treatment during the study will be documented in CRF.

6.5.1. Allowed Concomitant Therapy for LN Cohort

During the course of the study, participants in the LN cohort will receive allowed concomitant therapy consistent with the standard of care for induction and maintenance treatment of LN.

- For participants who have not started corticosteroid induction treatment prior to Screening:
 - Participants will receive a cumulative dose of 1 gram of methylprednisolone IV administered in 1 or multiple divided doses or oral equivalent during the Screening Period (prior to Day 1).
 - During the Screening Period and no later than Day 2, all participants will receive oral corticosteroids with prednisone or prednisone equivalent with starting doses as outlined in **Table 10**. The starting minimum and maximum dose allowed are 30 mg/day and 60 mg/day, respectively. A corticosteroid taper will commence on Week 2 (Day 14). From Week 12 to Week 26, the target dose is 7.5mg/day. Following Week 26, participants may remain on 7.5 mg/day or continue to taper at the clinical discretion of the Investigator until Week 46. From Week 46 to Week 50, the dose of corticosteroids must not be changed.
 - During the Screening Period and no later than Day 1, participants will receive a cumulative dose of 1 to 1.5 g/day of MMF any time after completion of the IV

methylprednisolone during the Screening Period and no later than Day 1. The dose can be administered in multiple divided doses. Participants will continue to receive 1 to 1.5 g/day for 1 week.

- After receiving 1 to 1.5 g/day for 1 week, the dose will be increased per the discretion of the Investigator to a cumulative dose of 2 to 3 g/day of MMF no later than by Week 4 (Day 28). The dose can be administered in multiple divided doses. Participants will continue to receive 2 to 3 g/day of MMF until Week 50 after which it may be decreased or discontinued based on the Investigators' judgment and the Kidney Disease Improving Global Outcomes (KDIGO) clinical practice guidelines ([KDIGO, 2021](#)).
- For participants who have initiated corticosteroid induction treatment prior to Screening and do not meet Exclusion Criterion 20 (Section [5.2.2](#)):
 - If the participant already received methylprednisolone IV \geq 1 g or equivalent and is receiving MMF \geq 2 g/day prior to Screening, then methylprednisolone IV will not be given. The participant may continue the current MMF dose during Screening and during the treatment period the dose of MMF should be adjusted to achieve 2 to 3 g/day no later than Day 28 (4 Weeks). MMF will be continued at 2 to 3 g/day until Week 50, after which it may be decreased or discontinued based on the Investigator's judgment and the KDIGO clinical practice guidelines ([KDIGO, 2021](#)).
 - If the participant already received methylprednisolone IV \geq 1 g or equivalent and is receiving MMF $<$ 2 g/day prior to Screening, then methylprednisolone IV will not be given and the MMF dose will be increased during the Screening Period (no later than Day 1) to a cumulative dose of 1 to 1.5 g/day. Participants will continue to receive 1 to 1.5 g/day for 1 week after which the MMF dose will be increased per the discretion of the Investigator to 2 to 3 g/day to be achieved no later than Week 4 (Day 28). These doses can be administered in multiple divided doses. Participants will continue to receive 2 to 3 g/day until Week 50, after which it may be decreased or discontinued based on the Investigator's judgment and the KDIGO clinical practice guidelines ([KDIGO, 2021](#)).
 - If a participant is already receiving prednisone or prednisone equivalent, the dose will be continued until Day 2 at which time prednisone or prednisone equivalent should be administered (the minimum and maximum dose allowed are 30 mg/day and 60 mg/day, respectively) as outlined in [Table 10](#). The prednisone dose will be tapered starting on Week 2 (Day 14) according to the schedule. From Week 12 to Week 26, the target dose is 7.5 mg/day. Following Week 26, participants may remain on 7.5 mg/day or continue to taper at the clinical discretion of the Investigator until Week 46. From Week 46 to Week 50, the dose of corticosteroids must not be changed.

Table 10: Corticosteroid Taper for Participants With Lupus Nephritis

	Prednisone or Equivalent Dose (mg/day) According to Baseline Body Weight			
Study week	40 to 60 kg	61 to 80 kg	81 to 100 kg	> 101 kg
Screening to Week 2 ^a	30	40	50	60
2	25	35	40	50
4	25	30	30	40
6	20	25	20	30
8	15	20	15	20
10	10	15	10	10
12 ^b	7.5	7.5	7.5	7.5

^a The minimum and maximum starting doses of prednisone are 30 mg and 60 mg, respectively.

^b From Week 12 to Week 26, the target dose is 7.5 mg/day. Following Week 26, participants may remain on 7.5 mg/day or continue to taper at the clinical discretion of the Investigator until Week 46. From Week 46 to Week 50, the dose of corticosteroids must not be changed.

Other considerations regarding MMF dosing:

- An equivalent dose of enteric-coated mycophenolic acid sodium (MPS) may be used instead of MMF (ie, 360 mg dose MPS is equivalent to a 500 mg dose of MMF)
- Investigators may adjust the dosage of MMF due to tolerance or AEs. After the symptoms resolve, the Investigator should attempt to increase MMF (or equivalent) to the goal level. If symptoms return, then the participant should be continued on the highest tolerable dose.
- Any changes to the dose of MMF and the justification will be documented in the CRF.

Other considerations regarding the corticosteroid taper:

- All participants will have a scheduled corticosteroid taper starting on Day 14. Participants will reduce their prednisone dose according to their baseline body weight over 10 weeks until the dose is 7.5 mg/day by Week 12 (Table 10). From Week 12 to Week 26, the target dose is 7.5 mg/day. Following Week 26, participants may remain on 7.5 mg/day or continue to taper at the clinical discretion of the Investigator until Week 46. From Week 46 to Week 50, the dose of corticosteroids must not be changed.
- Deviations from the scheduled corticosteroid taper for any reason other than Renal Flare or Extrarenal SLE Flare will confound interpretation, so every attempt should be made to adhere to the tapering schedule.
- If disease is too clinically active in the opinion of the Investigator to begin the corticosteroid taper after Week 2, then the participant may continue to receive his or her initial corticosteroid dose for up to an additional 28 days. Similarly, participants who have started the taper and whose disease is too clinically active to continue

tapering, may remain at the same taper dose achieved for up to an additional 28 days. Failure to achieve the corticosteroid taper by Week 12 will not be considered as Treatment Failure and will be captured as a secondary endpoint.

- However, the prednisone dose may NOT be increased beyond the taper dose achieved unless participant meets the protocol-defined criteria for Renal Flare (Section 3.2.1) and/or Severe Extrarenal SLE Flare (Section 3.2.2) in which case these participants will receive additional standard of care therapy and will be included as Treatment Failures.

